#### **Expected total duration**

The total duration of the study including all the phases reported is approximately 2 months.

#### **Statistical processing**

Processing of descriptive data of the subjects (age, weight and height).

Evaluation of intra and inter examiner agreement by means of weighted Cohen's K with use of sampling evaluation divided into 3 intervals (+1, 0, -1) and 7 intervals (+3, +2, +1, 0, -1, -2, -3).

The Myoton data are processed by subtracting the average data of the three measurements (automatically carried out by the instrument) of the right limb from that of the left. The data obtained is categorized into 3 levels to be compared, again using weighted Cohen's K, with the data from the manual evaluation.

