The direct manual evaluation of the tension of the ITB certainly turns out to be more specific (valid/accurate) but arises doubts as to how reproducible it can be.

The proposed study will try to investigate the reliability of direct palpation of the ITB, investigating the reproducibility of the intra- and inter-examiner evaluation performed on the same day (intra-day) and validate the result of the palpatory examination with an instrument that measures tissue tension. It will also be evaluated whether concordance can be improved by appropriate training.

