#### **Description of the phases**

I phase - The two examiners together with the principal investigator perform 2 hours of training to standardize the sampling method (localization of the point to be evaluated of the ITB and intensity of pressure of the fingertips to be used) and discussion on the tension gradation detected on the ITB with some volunteers.

II phase - The recruitment will be carried out through the search for volunteers among the students of the OSCE-Bologna school of osteopathy, through announcement in the classroom and publication of the

recruitment in the FB social group of the school (OSCE planet) and WhatsApp groups of students organized by year.

III phase - First sampling of manual evaluation only, using a sample of 40 subjects (both limbs), as proposed in the literature (Patijn 2019).

The operators identify if there is an equal or different stiffness between the right and left ITB.

There will be a double evaluation for each sampling session: 1) if there is a uniformity of the tension between the two sides, or if there is a prevalence on one side; 2) quantification of the difference, if present, with a graduation in 3 levels.

In the first sampling, the examiner will indicate with + 1 a greater tension on the right side; - 1 on the left side; 0 if there are no significant differences.

The second sampling consists in identifying, when present, the graduation of the tension difference between the two sides, arlTBrarily divided into 3 levels. The examiner will then report:

+ 3 to indicate more tension on the right with a large difference from the left;

+ 2 to indicate greater tension on the right with a medium difference compared to the left;

+ 1 to indicate more tension on the right with a slight difference from the left;

0 to indicate an insignificant prevalence of tension on one side with respect to the other;

- 3 to indicate greater tension on the left with a large difference compared to the right;

- 2 to indicate greater tension on the left with an average difference with respect to the right;

- 1 to indicate more tension on the left with a slight difference compared to the right.

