#### Settings

The samplings will be made in a room with two beds arranged about 3 meters apart and two desks. A screen, placed on both beds, will cover the examined subject from the pelvis upwards. The same subject is evaluated, on the same day, by both examiners twice, approximately 20-60 min apart.

Two subjects at a time are made to enter the room where the two manual examiners are present; a third examiner will use the Myoton.

When the 2 subjects enter the room and lie down in a supine position on the bed, with both limbs uncovered, the operator keeps their feet together, with a Velcro strap, to symmetrize the major axis of the feet and indirectly rotation of the hip.

During this preparation of the subjects to test, the manual examiners are turned away so as not to identify the test subjects. Once the positioning is complete, the examiners turn around and have 15 seconds to evaluate the assigned subject (see figures - examiner A always evaluates the subject on the right bed first while examiner B the one on the left); once the subject has been evaluated and the subject's identification code has been reported on a piece of paper with the result of the evaluation which is placed in a container, they go on to evaluate the subject lying on the opposite bed and repeat the same procedure for recording and storing the data detected.

Once the manual evaluation test has been carried out by both examiners, the subjects, before getting off the bed, are evaluated by the examiner who uses the Myoton, following the instructions recommended by the manufacturer. The examiner traces an X with a pen on the evaluation point, about 5 cm proximally from the joint line and 1 cm from the anterior edge of the ITB, and then carries out the evaluation which automatically takes place through 3 impulses. The result is automatically stored in the preset instrument with the subject ID.

The parameters measured and stored are:

F – Natural oscillation frequency [Hz], which characterizes the tone or tension S – Dynamic stiffness [N/m]

D – Logarithmic decrease of the natural oscillation, which characterizes the elasticity R – Mechanical stress relaxation time (ms)

C – Ratio of strain and relaxation time, which characterizes the "Creep" (Deborah number).

At the end of all the evaluations, the examiner who manages the Myoton downloads the detected data onto the computer which is automatically stored on an Excel sheet.

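### The Myoton side difference is defined as left minus right, but the manual scales use plus for the right, so the validation kappa changes direction if the sign is carried through

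*Combined protocol and SAP*

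**What the plan says.** Statistical processing forms the Myoton side difference by "subtracting the average data of the three measurements (automatically carried out by the instrument) of the right limb from that of the left". It continues: "The data obtained is categorized into 3 levels to be compared", by weighted Cohen's kappa, with the manual result. The manual agreement analyses in the same section use a "sampling evaluation divided into 3 intervals (+1, 0, -1) and 7 intervals".

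The manual codes are defined in Description of the phases, III phase. On the three-level scale, "the examiner will indicate with + 1 a greater tension on the right side; - 1 on the left side". The seven-level scale has the same direction. Its plus end is "3 to indicate more tension on the right with a large difference from the left" and its minus end is "3 to indicate greater tension on the left with a large difference compared to the right".

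Settings lists five stored Myoton parameters (F, S, D, R and C). F is described as "Natural oscillation frequency [Hz], which characterizes the tone or tension". Statistical processing does not say which parameter enters the kappa.

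The comparison serves the aim, given at the end of the Introduction, to "validate the result of the palpatory examination with an instrument that measures tissue tension".

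**The concern.** The two measurements being compared have opposite stated directions. Taking the right limb from the left gives a positive number when the left is higher, whereas a positive manual score means the right is tighter. No section reverses one of them or says which of the three Myoton levels a positive difference becomes.

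If an analyst carries the sign straight into +1, 0 and -1 for a parameter that rises with tension, a subject whom both methods find tighter on the right is scored +1 by hand and -1 by the instrument. Good palpation would then look invalid, and palpation that tended to pick the wrong side would look valid. Finding this only after an unexpected negative kappa would mean changing the coding rule with the results in view. Because the parameter, cut-points and weights are also left open, that repair would be hard to tell apart from selection.

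**Working it through.** The plan gives no expected value for this kappa, so there is no figure to reproduce. The check covers the direction of subtraction and then its effect on kappa.

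**Direction.** Take an assumed subject with dynamic stiffness of 300 N/m on the right and 280 N/m on the left. The manual code for a tighter right side is plus. The rule in Statistical processing gives 280 - 300 = -20, which is minus. Right minus left would give 300 - 280 = +20, matching the manual code.

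**Effect on kappa.** Weighted kappa = 1 - Σ(w·O)/Σ(w·E). O and E are the observed and chance-expected cell proportions, and w is |i-j| for linear weights or (i-j)² for quadratic weights. The plan does not say which weights apply, so both are shown. With cut-points symmetric about zero (assumed), carrying the opposite sign through mirrors the Myoton columns. All margins and tables below are assumptions. Only n = 40 comes from the plan (phase VI).

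*Partial agreement, n = 40.* Rows are manual -1, 0, +1. Columns are the true Myoton side -1, 0, +1. The rows are [10, 3, 1], [3, 6, 3], [1, 3, 10], with margins 14/12/14.

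- Expected disagreement, the same under both codings because the margins are symmetric: linear 4(0.35 × 0.30) + 2 × 2(0.35²) = 0.42 + 0.49 = 0.91; quadratic 0.42 + 4 × 2(0.35²) = 0.42 + 0.98 = 1.40.
- Signs aligned: 12 subjects are one level apart and 2 are two levels apart. Linear observed (12 + 4)/40 = 0.40, so kappa = 1 - 0.40/0.91 = 0.560. Quadratic observed (12 + 8)/40 = 0.50, so kappa = 1 - 0.50/1.40 = 0.643.
- Signs as written: 12 are one level apart and 20 are two apart. Linear observed (12 + 40)/40 = 1.30, so kappa = 1 - 1.30/0.91 = -0.429. Quadratic observed (12 + 80)/40 = 2.30, so kappa = 1 - 2.30/1.40 = -0.643.
- Exact agreement falls from 26/40 (65%) to 8/40 (20%).

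*Partial agreement, right side dominant, n = 40.* The rows are [5, 2, 1], [2, 6, 3], [1, 3, 17]. Linear kappa goes from 0.57 to -0.31 and quadratic kappa from 0.64 to -0.48.

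*Perfect agreement with the sign carried through.* Kappa would be 1.00 if the signs were aligned. Here the weights are divided by their maximum, which leaves kappa unchanged.

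| Assumed manual margins (-1/0/+1) | Linear | Quadratic |
|---|---|---|
| 33/33/33% | 1 - (2/3)/(4/9) = -0.50 | -1.00 |
| 40/20/40% | 1 - 0.80/0.48 = -0.67 | -1.00 |
| 25/50/25% | 1 - 0.50/0.375 = -0.33 | -1.00 |
| 50/30/20% | 1 - 0.70/0.50 = -0.40 | 1 - 0.70/0.395 = -0.77 |

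Weighted kappa turns from positive to negative in every case. It is exactly negated only with quadratic weights and symmetric margins. Otherwise the negative value is smaller in size than the positive one it replaces.

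**The case against.** The strongest reply is that the plan never says the signed difference itself enters the kappa. Kappa needs the same categories for both methods, and the three manual levels are defined by side. A sensible analyst may therefore sort each Myoton result into right, none or left, and the order of subtraction then has no effect. In addition, no parameter is named, and for one that falls as tension rises the written order would happen to match the manual code. The wording may simply be a slip. The damage can be undone because the instrument data are stored by subject, and a strongly negative kappa would prompt a coding check. The single listed outcome does not involve the Myoton.

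All of this is fair, and it limits the severity. It does not remove the conflict. The only direction the plan states is opposite to its own manual coding, and a correct result depends on the analyst adding to or departing from the written rule. According to the Operators section, the person who tabulates and analyses the data stays outside the sampling room, so the written rule is what aligns the two codings.

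It is also fair that the unnamed parameter, the missing cut-points and the unstated weights are separate omissions. They would remain if the subtraction were the right way round, and they are not counted here as evidence for the sign problem.

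**Conclusion.** The concern holds. As written, the Myoton difference is left minus right, the manual scales use plus for the right, and nothing reconciles them. The reversal is conditional on two things: the sign is carried into the levels, and the chosen parameter rises with tension. When both apply, the illustrations with partial agreement move from about 0.56 to 0.64 down to between -0.31 and -0.64, depending on margins and weights. These sizes rest on assumed tables and symmetric cut-points, because the plan supplies neither margins nor cut-points.

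The effect is confined to the manual-versus-Myoton comparison. The intra- and inter-examiner kappas, the 0.60 threshold in phase V and the outcome of improved agreement after training are untouched. This should be fixed before phase VI, but it does not threaten the rest of the study.

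**What to change.** In Statistical processing, replace the subtraction rule with wording such as:

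> For [named Myoton parameter], the side difference is the right-limb mean minus the left-limb mean. It is coded +1 (right tighter) if above +d, 0 if between -d and +d, and -1 (left tighter) if below -d, matching the manual three-level scale. If the named parameter falls as tension rises, the sign is reversed.

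Reversing the subtraction and labelling the levels by side is the essential correction. The same edit should also settle the separate omissions: which of the five parameters is used, the value of d (fixed before phase VI data are seen), linear or quadratic weights, and which examiner's reading, from which round, is compared with the Myoton.

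The cost is a few sentences in the analysis section. Data collection does not change.

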# **Operators and Settings**

# Operators

Five operators will participate in the study:

- 1 operator, outside the sampling room, performs: registration by anonymizing the subject with an ID which is assigned to the subject by means of a piece of paper; distributes the information and collects informed consent to participate in the study; performs the post-collection processing (tabulation and statistics) of the collected data.

- 2 operators, inside the sampling room, carry out the manual sampling of the tension of the ITB;

- 1 operator, inside the sampling room, carries out the instrumental sampling (Myoton) of the tension of the ITB;

- 1 operator, inside the sampling room, who organizes the entry and exit of the subjects evaluated, giving the detection times.

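### The Myoton validity check reduces a continuous side difference to three levels with no cut-off, parameter or sign fixed, and on the likelier reading never uses the examiners' 1-2-3 grades

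*Combined protocol and SAP*

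**What the plan says.** The Introduction sets an aim to "validate the result of the palpatory examination with an instrument that measures tissue tension". Under Settings, the Myoton stores five continuous parameters (F, S, D, R, C). F is described as "Natural oscillation frequency [Hz], which characterizes the tone or tension" and S as dynamic stiffness; the other three describe other properties.

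Description of the phases (III phase) asks each examiner for two judgements: which side is tenser, if either, and then "quantification of the difference, if present, with a graduation in 3 levels". Positive scores mean the right side is tenser.

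Statistical processing analyses examiner agreement on both manual scales, "divided into 3 intervals (+1, 0, -1) and 7 intervals (+3, +2, +1, 0, -1, -2, -3". The Myoton difference is formed "by subtracting the average data of the three measurements (automatically carried out by the instrument) of the right limb from that of the left". Then: "The data obtained is categorized into 3 levels to be compared", "again using weighted Cohen's K, with the data from the manual evaluation". The section gives no cut-off, no rule for deriving one, no parameter and no kappa weights, and it plans no analysis of the uncut difference. Outcomes lists only the gain in agreement after training.

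**The concern.** A continuous side difference has no natural band that counts as equal, so someone must choose one. The manual zero has no numerical threshold either. The validity kappa therefore reflects two things: whether palpation tracks the instrument, and whether two undefined equal bands happen to be of similar width. A reader of the result could not separate them.

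If the three levels are +1, 0 and -1, half of the manual assessment (the grading) is recorded alongside the Myoton reading but never set against it.

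The direction of subtraction also runs opposite to the manual scale. Taken literally, good agreement would appear as disagreement. At stake is the interpretation of the only instrument-based result in the study.

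**Working it through.** **No figure to reproduce.** The protocol gives no expected kappa, no precision, and no SD or measurement error for the Myoton side difference. What follows illustrates sensitivity and is not a prediction.

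**Inputs.** From the protocol: 40 subjects in the VI phase, three Myoton levels, weighted kappa. Assumed: the examiner's impression and the Myoton difference are standard bivariate normal with correlation 0.6; the examiner calls zero within ±0.5 SD (38% of subjects); weights are linear.

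**Formula.** Weighted kappa = 1 - (observed weighted disagreement) / (weighted disagreement expected by chance), with weight 1 for adjacent levels and 2 for opposite levels.

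**Worked case, Myoton cut at ±0.5 SD.**
- Marginals: 0.3085, 0.3829, 0.3085.
- Cells: each same-side cell 0.1796; both-zero cell 0.1757; each of four adjacent cells 0.1036; each of two opposite cells 0.0254.
- Observed: 4 × 0.1036 + 2 × 2 × 0.0254 = 0.516.
- Expected: 4 × 0.3085 × 0.3829 + 2 × 2 × 0.3085² = 0.853.
- Kappa = 1 - 0.516/0.853 = 0.40.

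**Other cut-offs, same association.**

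| Cut-off (SD) | Called equal by Myoton | Kappa |
|---|---|---|
| 0.1 | 8% | 0.37 |
| 0.25 | 20% | 0.39 |
| 0.5 | 38% | 0.40 |
| 0.75 | 55% | 0.37 |
| 1.0 | 68% | 0.32 |
| 1.5 | 87% | 0.19 |
| 2.0 | 95% | 0.08 |

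**Other correlations** (examiner zero in 33%, cut-offs 0.43, 1.0 and 1.5 SD): 0.32, 0.25, 0.15 at correlation 0.5; 0.48, 0.38, 0.21 at 0.7; 0.64, 0.48, 0.24 at 0.85. The pattern is the same. It is sharper among central cut-offs when the examiner calls zero in 50%: at correlation 0.85, kappa runs from 0.48 (0.05 SD) to 0.63 (0.67 SD). The unstated weights matter too: at correlation 0.7 and 0.43 SD, kappa is 0.48 linear and 0.59 quadratic.

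**At n = 40, correlation 0.6.** The median gap between the best and worst cut-off is about 0.11 for cut-offs up to 0.75 SD and 0.20 for cut-offs up to 1.25 SD. The sampling SD of a single kappa is about 0.12.

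**Sign.** If the Myoton sign is reversed in the worked case, same-side and opposite cells swap. Observed disagreement becomes 4 × 0.1036 + 2 × 2 × 0.1796 = 1.133, and kappa = 1 - 1.133/0.853 = -0.33.

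**Grades and side bias.** Assigning grades 1, 2 and 3 at random within the correct side leaves the 3-level kappa unchanged at 0.40, because it does not use them. Spearman between the 7-level score and the uncut difference falls only from 0.57 to 0.52. Shifting the examiner by 1 SD towards one side leaves Spearman at 0.56, while kappa (0.5 SD cut) falls from 0.40 to 0.22. Each measure sees something that the other misses.

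**The case against.** The strongest reply is that this is a short specification gap in an analysis that is not the listed outcome, and that sensible cut-offs give almost the same kappa. Much of that stands. Kappa is nearly flat up to 0.75 SD, the gap there is about one sampling SD, and the steep fall needs bands that call most subjects equal. But without an SD for the Myoton difference, nobody can say where an unstated cut-off would fall.

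A reader might infer that the analyst will tune the band after seeing the ratings and so inflate validity. The protocol does not support this. Operators says that one person "performs the post-collection processing (tabulation and statistics) of the collected data", and the VI phase says that the processor does not take part directly in data collection. Neither says who sets the cut-off or when, and nothing suggests a search over cut-offs or parameters. The timing is simply unspecified.

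It can also be said that the grades might be covered after all, since the III phase uses three levels for slight, medium and large. If Statistical processing meant that, side and zero would drop out and cut-offs would still be missing. The +1, 0, -1 reading is likelier, but the text should settle it.

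Finally, a reader might conclude that kappa should give way to a correlation. It should not: a rank correlation measures association and misses systematic side bias.

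**Conclusion.** The concern holds at moderate strength. The only analysis serving the validity aim leaves the cut-off, the parameter and the sign alignment open. On the likelier reading it also leaves the 1-2-3 grades uncompared with the instrument. Under the assumed normal model with correlation 0.6, the choice of band matters little up to 0.75 SD and substantially from 1 SD upwards. A sign mismatch would turn the result negative. These sizes rest on assumed correlations, manual-zero rates and linear weights; the protocol supplies none of them.

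The before-and-after training comparison is unaffected. The stronger claim that a rank correlation would expose a failed grading is not supported: a fall from 0.57 to 0.52 could not be told apart from chance with 40 subjects.

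**What to change.** In Statistical processing:

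1. Name one Myoton parameter for validity in advance. F is the natural choice because Settings itself ties it to tension; S can be supportive and D, R and C descriptive.
2. Code the difference right minus left, to match the manual scale.
3. Add a Spearman or Kendall tau-b correlation, with 95% bootstrap CI, between each examiner's 7-level score and the uncut difference. Use first-round ratings, since the second round is manual only.
4. Keep the 3-level weighted kappa beside it as the agreement measure. State what the three levels are, state the weights, fix the cut-off before the manual ratings are seen, and show kappa over a range of cut-offs.
5. To look at the grading, report the absolute Myoton difference by manual grade. This would be descriptive. With assumed grade thresholds of 0.5, 1.0 and 1.6 SD, about 30%, 21% and 11% of subjects fall in grades 1, 2 and 3, or roughly 12, 8 and 4 of 40.

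The cost is a few lines of text and one or two more statistics to report. No new data are needed.
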